4.6.7. Anticoagulation Treatment

Anticoagulation treatment is reported as part of the concomitant medication and occur prior to treatment, and at any time post treatment. The determination of whether a patient has resumed anticoagulant treatment after and exanet administration will be characterized with two complementary methods as follows:

- Patients receiving any anticoagulant therapy given after andexanet treatment, either
 parenterally (e.g., enoxaparin, dalteparin, heparin, certoparin, nadroparin, fondaparinux)
 or orally (e.g., warfarin, rivaroxaban, apixaban, edoxaban, dabigatran, phenprocoumon,
 phenindione) for any duration at any dose up to the 30-day follow visit.
- Patients receiving any oral anticoagulant starting after the initiation of the andexanet bolus, and continuing for the duration of the follow-up period through either the Day 30

visit or death. Note – for patients enrolled prior to the implementation of Protocol Amendment 4 (for whom date of discontinuation was not indicated in the database), derivation rules will be specified.

In addition to the above, the following variables will be analyzed:

- Indication for Anticoagulation: Patients may receive anticoagulation for multiple reasons. Indication will be defined as follows:
 - Arterial Thromboembolism: Any concomitant medication with indication term that contains "Arterial Thromboembolism, CVA, Secondary Stroke, Cerebrovascular Accident, PAD, Clot Related to Transplant Kidney/Pancreas."
 - Atrial Fibrillation
 - VTE: Any concomitant medication with indication term that contains "Venous Thromboembolism Prevention, Venous Thromboembolism Treatment, Pulmonary Embolism."
 - Other: Any concomitant medication with indication term that contains "ARTIFICIAL HEART VALVE, PORTAL VENOURS THROMBOSIS, S/P CABG WITH MAZE PROCEDURE FOR A-FIB, STROKE, PACEMAKER, ATRIAL FLUTTER, THROMBOPHLEBITIS, GUILLAIN-BARRE SYMDROME, THROMBOCYTHEMIA, THROMBOPHILIA, ARRHYTHMIA, ATRIAL FLUTTER, BRIDGING OF COUMADIN FOR MVR-S/P LAMINECTOMY, MECHANICAL MITRAL AND AORTIC VALVE, TRANSTHYRETIN AMYLOIDOSIS, PERIPHER VASCULAR DISEASE + STENT."
- Start Date and Time for Anticoagulation: Date and Time of first anticoagulation prior to andexanet treatment
- Number of Hours from Anticoagulation: Numbers of hours from last dose of anticoagulation to start of andexanet dose
- Start Date and Time for Re-anticoagulation: Date and Time of first anticoagulation post start of and examet treatment. If time is missing, report only the date.
- Number of Days to Re-Anticoagulation: Numbers of days from first dose of andexanet to re-start of anticoagulation treatment (no days = intck('day', date of first andexanet dose, date re-start anticoagulation).
- Was the Re-anticoagulation Dose Therapeutic (yes, no)
- Reason for Re-anticoagulation (see reason on CR#230, include therapeutic and non-therapeutic reasons. For other, use other non-therapeutic or other therapeutic)

4.6.8. Thrombotic Events

Thrombotic events (TE) will be adjudicated by the EAC (see CRF#122). A patient may have multiple Thrombotic events.

- Adjudicated Thrombotic events will be rated as follows:
 - 0 = If the event type is adjudicated as Death or Other AE. These events are not considered to be TEs.
 - 0 1 = If the event type is adjudicated as Myocardial Infarction; Ischemic Stroke (Stroke with adjudicated code of 021 for Ischemic), Transient Ischemic Attack, Deep Vein Thrombosis, Pulmonary Embolism or Arterial Systemic Embolism) and the adjudication decision is "Agree". These events are considered to be TEs.
- Thrombotic Event Type: Defined based on CRF#122 and coded as follows:
 - CVA = Ischemic Stroke
 - o MI = Myocardial Infarction
 - o DVT = Deep Vein Thrombosis
 - PE = Pulmonary Embolism
 - o ASE = Arterial Systemic Embolism
 - TIA= Transient Ischemic Attack.
- · Date and Time of Thrombotic Event
- Time to Thrombotic Event: Time elapsed from first dose of and examet treatment to the Date time of TE. Time to thrombotic events will be calculated in hours and days. Time to Thrombotic Event will also be presented as categorical variable. The following categories will be used: 0-12 hours; >12 hours and < 4 days; 4 to 30 days.

Per correspondence with FDA during label negotiations prior to FDA approval of the label supplement on 06 March 2020, an additional definition of Thrombotic Events includes the following list of adverse event terms:

- "Acute myocardial infarction"
- "Myocardial infarction"
- "Myocardial ischaemia"
- "Troponin increased"
- "Troponin T increased"
- "Cardiac arrest"
- · "Cardio-respiratory arrest"
- "Cardiac failure"
- "Cardiac failure congestive"
- "Right ventricular failure"
- "Cardiac ventricular thrombosis"
- "Cerebrovascular accident"

- "Death"
- "Deep vein thrombosis"
- "Embolism venous"
- "Venous thrombosis limb"
- "Intracranial venous sinus thrombosis"
- "Ischaemic hepatitis"
- "Pulmonary embolism"
- "Acute respiratory failure"
- "Respiratory failure"
- "Embolic stroke"
- "Ischaemic stroke"
- "Sudden death"

- · "Cardiogenic shock"
- "Cerebellar infarction"
- "Cerebellar ischaemia"
- "Cerebral infarction"

- "Transient ischaemic attack"
- "Ventricular tachycardia" "Iliac artery occlusion" "Heparin-induced thrombocytopenia"

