4.6.4. Re-bleeding

Re-bleeding is defined as bleeding from the same or another anatomical site in the patient within 24 hours of initial and exanet treatment and after achieving initial good/excellent hemostasis.

Re-bleeding will be adjudicated by the EAC. The following variables will be analyzed:

- Did Re-bleeding Occur (yes, no)
- Site of Re-bleeding
- Start Date/Time of Re-bleeding
- Stop Date/Time of Re-bleeding
- Time to Re-bleeding: Numbers of days/hours from date time of first dose of andexanet treatment to the time of Re-bleeding.
- Treatment Received for Re-Bleeding
- Coagulation Factor Transfusion (yes, no)
- Hemostatic Treatments (yes, no)
- Packed Red Blood Cell Transfusion (yes, no)
- Use of Colloids and Crystalloids (yes, no)
- Other blood/coagulation Related Treatment (yes, no)

4.6.5. **Death**

- Did the Patient Die (yes, no)
- Date/time of Death
- Time to Death: Number of days/hours from inform consent to death.
- Cause of Death; Adjudicated cause of death will be first grouped as cardiovascular or Non-cardiovascular as adjudicated by the EAC. In addition, the sub-category as presented in CR#099 for Cardiovascular or non-cardiovascular reason need to be specified.
- Death Preceded by Myocardial Infarction, Ischemic Stroke (note to programmer: ischemic stroke sometimes was reported as Embolic Stoke), Deep Vein Thrombosis, Pulmonary Embolism, and/or Arterial Systemic Embolism.

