All deaths will be assessed, and the causes of death adjudicated, by the EAC. Deaths due to cardiovascular causes (i.e., resulting from MI, sudden cardiac death, heart failure, stroke, CV procedures, CV hemorrhage, and other CV causes) will be classified as related to bleeding or non-hemorrhagic.

Kaplan-Meier curve for time to death will be presented by treatment by FXa inhibitor, and exanet dose, and and exanet manufacturing process. Patients who discontinue the study prior to Day 30 with an unknown survival assessment will be censored at the time of the last visit. Also, patients that completed the study (i.e., Day 30) will be censored at Day 30.

In addition, the proportion of patients that died during the 30 day follow-up with exact 95% CI will be presented for the overall safety population, by age category, region, FXa inhibitor, bleeding type, and exanet dose, and exanet manufacturing process, and by age deciles. In addition, the cause of death will be summarized.

The relationship between anti-fXa and 30-day mortality, will be analyzed (in the safety population), using a logistic regression model, with Age included as a covariate.

- 30-day mortality will define Death as Death at any time (including deaths recorded after Day 30). A sensitivity analysis defining Death as above (died during the 30 day followup) will be performed as well.
- Age will be entered into the model using a cubic spline transformation to best reflect the relationship with mortality.

- The Full Model will be compared to the Reduced Model with a Likelihood Ratio Test. The Reduced Model will be rejected in favor of the Full Model if the Likelihood Ratio Test p-value is <0.05.
 - Reduced Model: includes Age (with cubic spline transformation)
 - Full Model: includes Age (with cubic spline transformation) and an indicator variable for anti-fXa at on-treatment Nadir < threshold (where the threshold is 30 ng/mL for the DOACs, and 0.10 IU/mL for Enoxaparin).
- The area under the receiver operating characteristic (AUC under ROC) with the 95% CI will be presented for the Full Model.
- Descriptive statistics, odds ratios with the corresponding 95% confidence intervals, and p-values from the models will be presented also.

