5.16.4. Thrombotic Events

Potential Thrombotic Events (TEs) will be submitted by each Investigator for adjudication by the EAC using definitions pre-specified in the EAC Charter. The proportion of patients in the safety population who are adjudicated to have a TE by the independent EAC will be summarized. An exact 95% CI will be reported. Analysis will be performed for the safety patient population, by age category, sex, region, FXa inhibitor, bleeding type, andexanet dose, andexanet manufacturing process, medical history (i.e., atrial fibrillation (AF), Ischemic Stroke or Transient Ischemic Attack (CVA/TIA), Venous Thrombotic Event (VTE), or Cancer); and the type of TE (i.e., Ischemic Stroke (CVA), Myocardial Infarction (MI), Deep Vein Thrombosis (DVT), Pulmonary Embolism (PE), Arterial Systemic Embolism (ASE), and Transient Ischemic Attack (TIA). Also, the age, sex, FXa inhibitor, type of bleeding, previous history of TE, hospital length of stay and deaths for patients with and without thrombotic events will be compared.

An additional summary of possible TEs will be presented using a broader definition of TEs as recommended by FDA. See Section 4.6.8 for further details on the selection of events. The proportion of patients in the safety population who have a TE by this broader definition will be summarized. An exact 95% CI will be reported.

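### SAP 4.6.8 has no rule that counts a death with an adjudicated thrombotic cause as a thrombotic event, and the additional term list is not guaranteed to contain every adjudicated event

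*SAP*

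**What the plan says.** SAP 4.6.8 rates each adjudicated event. The value is 0 under this rule: "If the event type is adjudicated as Death or Other AE. These events are not considered to be TEs". The value is 1 for myocardial infarction (MI), ischemic stroke, transient ischemic attack (TIA), deep vein thrombosis (DVT), pulmonary embolism (PE) or arterial systemic embolism (ASE) when "the adjudication decision is 'Agree'. These events are considered to be TEs". The section adds: "A patient may have multiple Thrombotic events".

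Cause of death is a separate variable. In SAP 4.6.5, "Adjudicated cause of death will be first grouped as cardiovascular or Non-cardiovascular as adjudicated by the EAC", with sub-categories taken from form CR#099. SAP 5.16.3 describes cardiovascular deaths as those "resulting from MI, sudden cardiac death, heart failure, stroke" and further causes, and splits them into bleeding-related and non-hemorrhagic. SAP 4.6.5 also defines a variable that begins "Death Preceded by Myocardial Infarction, Ischemic Stroke" and continues with DVT, PE and ASE.

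The main TE estimate is in SAP 5.16.4: "The proportion of patients in the safety population who are adjudicated to have a TE by the independent EAC will be summarized". It has an exact 95% CI and is repeated over many subgroups. The same section compares patients with and without TEs on several features, including deaths. A second summary is made "using a broader definition of TEs as recommended by FDA"; its terms are listed in 4.6.8.

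**The concern.** Thrombosis is the main safety question for an agent that reverses anticoagulation. The protocol (9.3) makes TEs of any severity adverse events of special interest.

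Under SAP 5.16.4, potential TEs reach adjudication when an investigator submits them. The EAC judges cause of death as a separate task, and the SAP plans separate listings of cause of death by investigator and by committee (16.2.7.5a and 16.2.7.5b), so the two can differ. Suppose the EAC attributes to MI or PE a death that the investigator did not submit as a TE. The patient then has a Death record, scored 0, and no TE record. By the written rule this patient has no TE, in the overall proportion and in every subgroup. In the comparison of deaths by TE status, the death falls on the side without TE, which weakens any association between TE and death.

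The second summary could be expected to act as a safety net, because it is called broader. It is a fixed term list, however, and no sentence adds the adjudicated TEs to it.

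**Working it through.** The documents give no TE count, TE rate or TE-based sample size, so there is no planned figure to reproduce. The check has three parts.

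**1. Which patients the rule misses.** The rating is per event, so four cases cover a patient who dies of a thrombotic cause:
- An agreed TE record and a Death record: ratings 1 and 0, so the patient counts as having a TE.
- An agreed TE record only: rating 1, counted.
- A Death record only, with a thrombotic adjudicated cause: rating 0, not counted.
- A record of a TE type whose decision is not Agree: SAP 4.6.8 gives neither 0 nor 1.

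The third case is the gap. SAP 4.6.5, 4.6.8, 5.16.3 and 5.16.4 contain no sentence that closes it. The variable on deaths preceded by a TE in 4.6.5 does not enter the TE proportion.

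**2. Size.** The denominator is N = 477 (SAP 1.0), taken here as the safety population. Let x be the number of patients counted by the rule and k the number in the third case. The reported proportion is x/477 and the complete one is (x + k)/477, so the shortfall is k/477:
- k = 1: 1/477 = 0.21 points
- k = 2: 2/477 = 0.42 points
- k = 5: 5/477 = 1.05 points
- k = 10: 10/477 = 2.10 points

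Both x and k are assumptions. With exact (Clopper-Pearson) 95% CIs:

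| x | k = 0 | k = 5 | k = 10 |
|---|---|---|---|
| 24 | 5.03% (3.25 to 7.39) | 6.08% (4.11 to 8.61) | 7.13% (4.99 to 9.82) |
| 48 | 10.06% (7.51 to 13.12) | 11.11% (8.43 to 14.28) | 12.16% (9.36 to 15.43) |
| 72 | 15.09% (12.00 to 18.63) | 16.14% (12.95 to 19.76) | 17.19% (13.91 to 20.88) |

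If every fatal TE has its own agreed record, k = 0 and nothing changes.

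**3. Does the term list contain the adjudicated types?** The list in SAP 4.6.8 has 32 terms. Set against the six adjudicated types:
- MI, ischemic stroke, TIA, DVT and PE each have a directly matching term.
- ASE has none. The only peripheral arterial term is Iliac artery occlusion. The terms that name an embolism are Embolism venous, Pulmonary embolism and Embolic stroke, which describe other events.

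An agreed ASE coded to any other term would count in the adjudicated definition and not in the one called broader. More generally, so would any adjudicated TE whose adverse event is coded to an unlisted term. The list does include Death and Sudden death.

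**The case against.** The strongest reply is that recognised fatal TEs very probably have their own records. Protocol 9.3 requires TEs of any severity to be reported within 24 hours. Protocol 11.7.2 sends all potential TEs to the EAC. TEs and deaths are separate adjudication items (SAP 3.4). SAP 4.6.5 tabulates deaths preceded by a TE, which presupposes TE records in patients who died. Scoring the type Death as 0 may only keep deaths on the same form from being counted as TEs. The EAC Charter, which holds the TE definitions, and the forms are not among the documents and may settle the matter. The TE summaries are descriptive, and no primary test depends on them.

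Most of this stands. It makes a small k likely and allows k = 0. It does not cover a death that only the EAC attributes to a thrombotic cause, because the route to TE adjudication is investigator submission.

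A reader might infer from the rule that all fatal TEs are dropped, or that an event counts only if the patient survives. The documents do not support that: the rating has no condition on outcome, and a Death record does not cancel an agreed TE record. A reader might also infer that the broader list certainly omits adjudicated TEs. That is not shown either. Five of six types are matched, no actual omitted case is known, and fatal events coded as Death or Sudden death do appear in the second summary, though not in the main proportion.

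**Conclusion.** The gap is real but conditional. As written, a patient whose sole thrombotic record is a death is scored as having no TE, even if the EAC gives a thrombotic cause of death. The shortfall is 0.21 points per such patient. For an assumed 0 to 10 patients it is 0 to 2.1 points. The documents do not allow the number to be determined, and it may be zero. The error can go only one way, towards a lower TE proportion.

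The broader definition is not guaranteed to contain every adjudicated TE. At the level of event type, the gap is ASE coded to a term other than Iliac artery occlusion.

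These conclusions assume that the safety population is the 477 locked patients and that the EAC Charter has no rule that closes the gap. This is a modest improvement to a descriptive safety summary, and no efficacy conclusion depends on it.

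**What to change.** In SAP 4.6.8, add a patient-level rule: TE = 1 if the patient has any agreed TE record, or if the EAC-adjudicated cause of death is MI, ischemic (non-hemorrhagic) stroke, PE or another thrombotic or embolic cause. Use the bleeding versus non-hemorrhagic classification in 5.16.3 to keep hemorrhagic stroke deaths out. This matters in a population enriched for intracranial hemorrhage. Show fatal and non-fatal TEs separately. State also how a TE-type event with a decision other than Agree is rated.

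Before programming, confirm on CR#099 that the sub-categories identify these causes. The list in 5.16.3 names stroke without a subtype and does not name PE.

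In SAP 5.16.4, define the broader summary as any listed term or any adjudicated TE, and keep the list-only count beside it as the version recommended by FDA.

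The cost is SAP wording, a check of one form and minor programming with adjudication data already collected. The TE proportion may become slightly less favourable.

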5.0 STATISTICAL METHODS

5.1. General Considerations

All hypothesis tests will be 2-sided and reported at the 0.05 significance level. All CIs will be 2-sided and reported at the 95% confidence level unless stated otherwise. P-values will be rounded to 3 decimal places. P-values less than 0.001 will be presented at p < 0.001.

For continuous variables, the number of non-missing observations, mean, median, quartiles, standard deviation, minimum, maximum, and 95% confidence interval (CI) will be presented unless stated otherwise. Means, medians, quartiles, and 95% CI will be displayed to 1 more decimal place than the raw data and the standard deviation will be displayed to 2 more decimal places. The minimum and maximum will be displayed to the same number of decimal places as reported in the raw data. For categorical variables, the number of observations, the number of events, and percentages of events with the 95% CI will be reported. Descriptive summaries will be presented for the efficacy population as well as for the individual subgroup analyses.

It is anticipated that all statistical analyses will be performed using SAS Version 9.4 (SAS Institute, Inc., Cary NC) or higher. Additional software may be used for the production of graphics and for statistical methodology not provided by SAS. All summaries and analyses documented in this Statistical Analysis Plan (SAP) will be presented in the final integrated CSR. The CSR may also contain additional tables or statistical tests as warranted by the data obtained. The justification for any such additional analyses will be fully documented in the CSR.

5.2. Analysis Populations

5.2.1. Safety Population

The Safety Population will consist of all patients treated with any amount of andexanet.

5.2.2. Efficacy Population

The Efficacy Population will include all patients in the Safety Population who meet all of the following criteria:

- Are determined by the EAC to meet the clinical bleeding inclusion criteria.
- Have a baseline anti-fXa level
- Baseline anti-fXa level of at least 75 ng/mL for apixaban and rivaroxaban, 40 ng/mL for edoxaban, and 0.25 IU/mL for patients receiving enoxaparin.

5.2.3. High Risk ICH Population

The High Risk ICH analysis population will include all ICH patients in the efficacy Population with any of the following:

• For intracerebral/intraparenchymal bleeding, volume of hematoma > 3 cc.

- For subdural bleeding, thickness of hematoma > 10 mm or midline shift > 5 mm.
- For subarachnoid bleeding, thickness of hematoma > 10 mm.

5.3. Appropriateness of Primary Efficacy Endpoints

Anti-fXa activity is considered a biomarker reasonably likely to predict clinical benefit based on the following data:

- The direct FXa inhibitors have similar structural, stoichiometric, pharmacokinetic (PK), and functional properties.
- Anti-fXa activity is a direct measure of the inhibition of the enzymatic activity of FXa by
 anticoagulants in the FXa class and correlates with the plasma concentrations of
 rivaroxaban, apixaban, and edoxaban (e.g., 100 ng/mL of plasma apixaban = 100 ng/mL
 anti-fXa activity of apixaban).
- Data from the clinical studies of currently approved direct FXa inhibitors (apixaban, rivaroxaban, edoxaban) clearly demonstrate a correlation between plasma concentrations of the FXa inhibitor and increased bleeding.
- Data from both the FXa inhibitor clinical studies and the andexanet clinical program demonstrate a 1:1 correlation between FXa inhibitor concentrations and anti-fXa activity.
- In both nonclinical and clinical studies, increases in anti-fXa activity correlate with decreases in thrombin generation.
- There is consistency across all three direct FXa inhibitors regarding the correlations between anti-fXa activity levels and free-fraction of the inhibitors, thrombin generation, and the Activated Clotting Time (ACT) in the andexanet clinical studies.
- In animal models of anticoagulant-exacerbated bleeding, reduction in anti-fXa activity correlates with reduction in blood loss.

For Hemostatic efficacy assessment, because of the heterogeneity of bleeding (e.g., different anatomic locations, different mechanism and severity of injury), it was not possible to use a single type of measurement to evaluate all bleeding types. The efficacy variable of "effective hemostasis" (Protocol Amendment 4 Appendix B) chosen for this study was an endpoint developed in collaboration with the FDA and agreed to by the Committee for Medicinal Products for Human Use (CHMP) during scientific advice received in 2014. The criteria for this endpoint were based on those used in the study by Sarode, et al (2013) [1], which was a registration trial for a reversal agent for warfarin-induced bleeding. The scoring system for effective hemostasis allows for different types of assessments for different bleeding types (e.g., head CT or MRI for ICH, corrected Hb and hematocrit for non-visible bleeding, and clinical assessments for visible, muscular, and skeletal bleeding). Because the criteria for determination of hemostatic efficacy are largely based on objective measures (CT/MRI measurements, Hb corrected for transfusion), the potential for bias is reduced (to further reduce the potential for bias, bleeds that were more

dependent on subjective assessments of clinical hemostasis [i.e., musculoskeletal bleeds, intra-articular bleeds, visible bleeds] were excluded with the implementation of Protocol Amendment 4). In addition, an independent EAC adjudicated all endpoints blinded to the results of the anti-fXa evaluation.

